4.5. Multiple Comparisons

Each endpoint for this study implicitly contains three hypothesis tests based on comparisons between study treatments: i) 75/2.5 dose vs placebo, ii) 37.5/2.5 dose vs placebo, iii) 37.5/2.5 dose vs 75/2.5 dose. The sequential testing order of these hypotheses will be:

1. 75/2.5 dose vs placebo for HB(4%),
2. 37.5/2.5 dose vs placebo for HB(4%),
3. 75/2.5 dose vs placebo for AHI(4%),
4. 37.5/2.5 dose vs placebo for AHI(4%),
5. 75/2.5 dose vs placebo for ODI(4%),
6. 37.5/2.5 dose vs placebo for ODI(4%),
7. 37.5/2.5 dose vs 75/2.5 dose for HB(4%),
8. 37.5/2.5 dose vs 75/2.5 dose for AHI(4%), and
9. 37.5/2.5 dose vs 75/2.5 dose for ODI(4%).

All hypothesis tests will test that the two-sided p-value is less than 0.05.

All hypothesis tests for secondary endpoints will be reported using the nominal 0.05 two-sided alpha level.

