2.2.2. Secondary Endpoints

The secondary efficacy endpoints are as follows:

- Change in $\log_{10}(\text{HB}[4\%] + 1)$, 37.5/2.5 dose vs. placebo and vs. 75/2.5
- Change in Apnea Hypopnea Index (AHI) 4%
- Change in Oxygen Desaturation Index (ODI) 4%

- Total time with $\text{SaO}_2 < 90\%$, PSG nights
- Proportion of participants with $\geq 50\%$ reduction in AHI(4%), HB(4%), and ODI(4%)

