6.2.2. AHI(4%)

Multiple comparisons will be performed as described in Section 4.5. A repeated measures model (see Section 4.7) will be used to model change in AHI(4%) from baseline. Model based LS mean estimates will be provided for the following:

- mean change by study treatment (75/2.5 dose, 37.5/2.5 dose, placebo),
- difference in mean change between study treatments (75/2.5 dose vs placebo, 37.5/2.5 dose vs placebo, and 75/2.5 dose vs 37.5/2.5 dose) with 95% confidence intervals and respective p-values (for null hypothesis).

Descriptive statistics for the reported value and change from baseline in AHI(4%) will be presented by study treatment.

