6.2.3. ODI(4%)

Multiple comparisons will be performed as described in Section 4.5. A repeated measures model (see Section 4.7) will be used to model change in ODI(4%) from baseline. Model based LS mean estimates will be provided for the following:

- mean change by study treatment (75/2.5 dose, 37.5/2.5 dose, placebo),
- difference in mean change between study treatments (75/2.5 dose vs placebo, 37.5/2.5 dose vs placebo, and 75/2.5 dose vs 37.5/2.5 dose) with 95% confidence intervals and respective p-values (for null hypothesis).

Descriptive statistics for the reported value and change from baseline in ODI(4%) will be presented by study treatment.

¹ Only 75/2.5 dose vs placebo is part of the primary outcome. The 37.5/2.5 dose vs placebo and 37.5/2.5 dose vs 75/2.5 dose are secondary outcomes.

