6.2.4. Total time with SaO₂<90%

Multiple comparisons will be performed as described in Section 4.5. A repeated measures model (see Section 4.7) will be used to model total time with SaO₂<90%. Model based LS mean estimates will be provided for the following:

- mean change by study treatment (75/2.5 dose, 37.5/2.5 dose, placebo),
- difference in mean change between study treatments (75/2.5 dose vs placebo, 37.5/2.5 dose vs placebo, and 75/2.5 dose vs 37.5/2.5 dose) with 95% confidence intervals and respective p-values (for null hypothesis).

Descriptive statistics for the reported value and change from baseline in total time with SaO₂<90% will be presented by study treatment.

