9. SAMPLE SIZE AND POWER CALCULATIONS

A total of 30 patients will enter the 3-treatment crossover study. The study will have 80% power to detect a treatment difference on the primary endpoint at a two-sided 0.05 significance level, if the true difference between treatments on HB is at least -3.7 % min/h. This assumes that the within-participant standard deviation is 9 and a discontinuation rate of less than 20%.

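### SAP 4.5 lists nine hypotheses in a sequential order but gives no stop rule, so it is unclear which secondary results could be claimed

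*SAP*

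**What the plan says.** SAP 4.5 introduces a numbered list of nine hypotheses with "The sequential testing order of these hypotheses will be". In order, these are both doses against placebo on HB, then on AHI, then on ODI, followed by the low dose against the high dose on the same three endpoints. Two sentences close the section: "All hypothesis tests will test that the two-sided p-value is less than 0.05", and then "All hypothesis tests for secondary endpoints will be reported using the nominal 0.05 two-sided alpha level".

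Only the first step is primary. SAP 2.2.1 defines the primary endpoint as the high dose against placebo on HB. The footnote to the primary analysis adds: "The 37.5/2.5 dose vs placebo and 37.5/2.5 dose vs 75/2.5 dose are secondary outcomes". SAP 2.2.2 lists the AHI and ODI changes as secondary ("Change in Apnea Hypopnea Index (AHI) 4"%, and the ODI item after it). Steps 2 to 9 are therefore all secondary.

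The analysis sections refer back without adding a rule. SAP 6.1, 6.2.2 and 6.2.3 each say "Multiple comparisons will be performed as described in Section 4.5" and ask for p-values on all three contrasts unconditionally. SAP 6.2.1 points to the primary analysis. SAP 6.2.4 uses the same pointer for time with SaO₂ below 90% ("Multiple comparisons will be performed as described in Section 4.5. A repeated measures model (see Section 4.7) will be used to model total time"), although that endpoint is not in the list. SAP 6.2.5 does not mention 4.5. Protocol section 8 has no multiplicity rule.

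**The concern.** An order of testing matters only if a failed step has a consequence. SAP 4.5 gives the order and the level but not the consequence, and its last sentence then treats every step that could be gated as nominal.

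Suppose one step has p ≥ 0.05 and a later one has p < 0.05. On a fixed-sequence reading, the later result supports no confirmatory claim. On the literal reading, it is a result at the 0.05 level like any other. Two statisticians could label the same p-value differently, and the choice could be made after the data are seen. This touches the study's stated purpose: SAP 2.1.1 sets out to compare both doses with placebo and with each other. On HB, the low dose against placebo and against the high dose are steps 2 and 7.

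**Working it through.** The documents state no familywise error rate, so there is no planned figure to reproduce. The check compares the two readings under the global null (no difference between any treatments on any of the three endpoints).

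**Inputs**
- Nine tests: 3 contrasts × 3 endpoints, in the order of SAP 4.5.
- Two-sided 0.05 at each step (SAP 4.5), critical value 1.96.
- 30 participants, with discontinuation below 20% (SAP 9), so as few as 30 × 0.8 = 24.
- Correlation ρ between HB, AHI and ODI: **assumed**, since the documents give none. All three come from the same PSG night, so 0.7 to 0.95 is the main range, with 0 and 1 as limits. Equal variances and a common ρ are also assumed.

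**With a stop rule.** No later step is tested unless step 1 rejects, so

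P(any false rejection) = P(step 1 rejects) = 5%, whatever ρ is.

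**Without a stop rule.** For treatment *t* and endpoint *e*, let X(t,e) be standard normal, independent between treatments, with correlation ρ between endpoints. Each contrast is D = [X(t,e) − X(t′,e)] / √2, rejected if |D| > 1.96. Contrasts that share a treatment are correlated by construction, so the independence formula 1 − 0.95⁹ = 37% does not apply. Simulation with 2,000,000 draws per setting gives:

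| ρ | Step 1 | Any of steps 1–9 | Any of steps 2–9 | Step 1 fails, a later step has p < 0.05 |
|---|---|---|---|---|
| 0.7 | 5.0% | 25.0% | 23.5% | 20.0% |
| 0.8 | 5.0% | 22.7% | 21.4% | 17.7% |
| 0.9 | 5.0% | 19.5% | 18.6% | 14.5% |
| 0.95 | 5.0% | 17.3% | 16.7% | 12.3% |

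The columns agree: step 1 plus the last column gives the nine-test figure, for example 5.0% + 20.0% = 25.0% at ρ = 0.7. With a stop rule the last column is 0%.

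At the limits, the nine-test figure is about 12% as ρ approaches 1 (in effect, three pairwise contrasts on one endpoint) and about 32% at ρ = 0.

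**Small-sample check.** With crossover t-tests and pooled within-participant variance (60,000 trials per setting), the nine-test figure is 25.0% at ρ = 0.7 and 17.4% at 0.95, at both n = 30 and n = 24. With a separate variance for each contrast, closer to the unstructured covariance of SAP 4.7, it is 25.6% and 17.5% at n = 30.

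**The case against.** The strongest reply is that a sequential order, with every step at an unadjusted 0.05, is what a fixed-sequence procedure looks like. The closing sentence could mean only that no adjusted level is used and all p-values are shown, which such a procedure allows. Familywise error is then 5%, and the sole defect is an unwritten stop sentence. This stands as a tenable reading. A reader might infer from the 17–25% that the plan as conducted would inflate error to that level. The documents do not support that: the figure belongs to the ungated reading, under the global null, at an assumed correlation.

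A second reply is that the closing sentence already makes all secondary tests nominal. If so, the nine-step order has no function. The two replies cannot both hold: each leaves one part of 4.5 redundant or misleading, and the text does not say which.

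A third is that this is a 30-participant Phase 2 study with one primary contrast, and nothing in it promises familywise control over secondary endpoints. That limits the weight of the point. It does not remove the need for a plan that sets a testing order to say what the order does.

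A reader might also want to know how often the two readings would part if the drug works. That needs the power of step 1, and SAP 9 says "The study will have 80% power to detect a treatment difference on the primary endpoint at a two-sided 0.05 significance level". Its own inputs do not give that value. With n = 30 and 9 as the within-participant SD, 3.7 / (9 × √(2/30)) = 1.59, and Φ(1.59 − 1.96) is about 36%. With 9 as the SD of the difference, 3.7 / (9/√30) = 2.25, and power is about 61%. No figure for that case is offered here.

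**Conclusion.** The point holds as an unresolved rule, not as demonstrated error inflation. Neither document states a consequence for a failed step, and the last sentence of 4.5 works against the order above it. If a gate is intended, familywise error over the list is 5%. If the text is followed literally, it is about 17–25% under the global null for an assumed endpoint correlation of 0.95 down to 0.7. The direction does not depend on that assumption, since even a correlation of 1 gives about 12%.

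A reader might infer that the primary result is at risk. It is not: step 1 is tested at two-sided 0.05 on either reading. Protocol 1.1 and 4.1 speak loosely of primary endpoints comparing both doses, but the endpoint table in Protocol 3 and SAP 2.2.1 fix a single primary contrast. Estimates and confidence intervals are also unchanged. What changes is which secondary results can be claimed, and that should be settled before unblinding.

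**What to change.** In SAP 4.5, keep the sentence "All hypothesis tests will test that the two-sided p-value is less than 0.05", so that the two-sided 0.05 level stays on record for every test. Replace the last sentence of the section with:

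> Hypotheses 1–9 are tested in the listed order; confirmatory testing stops at the first p ≥ 0.05. All later p-values in the list, and all p-values for endpoints not in the list, are reported at the nominal two-sided 0.05 level and are descriptive.

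This also settles the pointer in SAP 6.2.4, because time with SaO₂ below 90% is then plainly descriptive, as are the responder and tertiary comparisons.

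The cost is SAP wording only; data collection, sample size and models stay as they are. The downside is that once a step fails, no later step can be claimed, however small its p-value.

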4.6. Data Derivations and Transformations

Study Day will be calculated as:

- Date of assessment – date of randomization + 1 for assessments done on or after date of randomization
- Date of assessment – date of randomization for assessments done before date of randomization

For each efficacy and safety endpoint, the baseline value will be calculated as the last non-missing value prior to randomization (except where unscheduled assessments are performed the baseline value should be the value recorded at Screening). Where applicable, change from baseline values will be calculated as:

Change from Baseline = assessment value – baseline value,

while the percent change from baseline values will be calculated as:

$$\text{percent change from baseline} = \frac{\text{change from baseline}}{\text{baseline value}} \times 100\%.$$

For the endpoints that look for the proportion of participants with $\geq 50\%$ reduction, participants will be assigned a visit level indicator:

$$\text{Indicator of } \geq 50\% \text{ reduction} = \begin{cases} 1 & \text{if percent change from baseline } \leq -50\% \\ 0 & \text{otherwise} \end{cases}.$$

4.7. Modeling for Select Endpoints

In Section 6, modeling will be used for comparisons between study treatments with respect to given endpoints using the PROC GLIMMIX procedure in SAS. The model will include study treatment and visit as fixed effects. Within participant variability (nested within treatment sequence) will be modeled using an unstructured (e.g., TYPE = UN, CHOL) covariance pattern. The unstructured covariance parametrized through its Cholesky root is to be used for logistic regression models and models in which convergence fails for the completely unstructured covariance. Point (e.g., mean, difference of means) and inferential (e.g., confidence interval, p-values) statistics will be provided using least squares (LS) methods. Unless otherwise stated, the link will be identity and the distribution gaussian.

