3.2.3. Dosing Schedule

There are 3 randomized crossover PSG nights. The participant will receive one treatment on each of the 3 PSG nights, separated by at least a one-week washout period. Dosing of the study treatment will occur immediately prior to lights out.

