4.2.2. Modified Intent-To-Treat Analysis (mITT) Set

The mITT Set comprises all participants who are randomized, take at least 1 dose of any of the study treatments, and have at least 1 measurement on the primary endpoint.

Participants will be analyzed for efficacy according to the randomly assigned treatment for each period.

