6.1. Primary Efficacy Analysis – HB(4%)

Multiple comparisons will be performed as described in Section 4.5. A repeated measures model (see Section 4.7) will be used to model change in $\log_{10}(\text{HB}[4\%] + 1)$ from baseline. Model based LS mean estimates will be provided for the following:

- mean change by study treatment (75/2.5 dose, 37.5/2.5 dose, placebo),

- difference in mean change between study treatments¹ (75/2.5 dose vs placebo, 37.5/2.5 dose vs placebo, and 75/2.5 dose vs 37.5/2.5 dose) with 95% confidence intervals and respective p-values (for null hypothesis).

If the model shows there is a visit (i.e., period) effect, then ad hoc analyses will be performed. A sensitivity analysis will be performed using the PP Set on the primary efficacy endpoint using the same methods described above and using HB(4%) with identity transform (i.e., without transform) on the mITT set.

Descriptive statistics for the reported value and change from baseline in $\log_{10}(\text{HB}[4\%] + 1)$ will be presented by study treatment. By taking the inverse transformations of the respective means, the geometric mean of HB(4%) + 1 and the ratio of the geometric mean to baseline will be reported.

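### SAP 4.7 leaves open the index of its unstructured covariance and any small-sample SE correction; indexed by visit and uncorrected, the nominal 5% primary test runs at about 7–8.5%

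*SAP*

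**What the plan says.** SAP 4.7 defines one model, fitted in PROC GLIMMIX, for the efficacy comparisons. On the mean structure: "The model will include study treatment and visit as fixed effects". On the covariance: "Within participant variability (nested within treatment sequence) will be modeled using an unstructured (e.g., TYPE = UN, CHOL) covariance pattern". The Cholesky form is reserved for the logistic models and for fits where the plain unstructured matrix does not converge. Inference is described only as using least squares methods. No denominator degrees-of-freedom method and no SE adjustment is named, and none is ruled out.

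The dimension of the matrix has to be inferred from SAP 3.2.3: "There are 3 randomized crossover PSG nights". SAP 6.1 refers back to 4.7 for the primary model and adds only this on visits: "If the model shows there is a visit (i.e., period) effect, then ad hoc analyses will be performed". Protocol section 8 gives no model. The required level is in SAP 4.5: "All hypothesis tests will test that the two-sided p-value is less than 0.05".

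**The concern.** Three models fit the wording: a residual matrix indexed by visit, a residual matrix indexed by treatment, or a participant random intercept. With 30 participants they are not interchangeable.

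Under visit indexing, the treatment contrast is a weighted combination of within- and between-participant information. The weights come from six estimated covariance parameters. The model-based SE treats those weights as known, so it is too small. Under treatment indexing in this near-balanced design, the contrast stays close to a mean paired difference and depends little on the estimated weights.

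At stake are the primary test, which heads the nine-step sequence in SAP 4.5, and the intervals for HB, AHI, ODI and time below 90% saturation. For DSST only interval width is affected, since SAP 7.5 plans no p-values. The planned sensitivity analyses would not expose a problem. The Per Protocol one repeats the model: "A sensitivity analysis will be performed using the PP Set on the primary efficacy endpoint using the same methods described above". The untransformed-HB one is given no different model.

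**Working it through.** **Inputs from the documents.** 30 participants and six sequences with five participants each (SAP 3.2.1); three periods; fixed effects for treatment and visit (SAP 4.7); two-sided 0.05 (SAP 4.5); discontinuation below 20% (SAP 9).

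**Assumed inputs.** Normal errors and a common correlation between nights of 0.5, 0.6 or 0.8. The documents give no correlation. The value 0.5 has a rationale: the outcome is a change from one shared baseline ("the baseline value will be calculated as the last non-missing value prior to randomization"). If all four nights have variance s² and pairwise correlation r, two change scores have covariance s²(1−r) and variance 2s²(1−r), so their correlation is 0.5 for any r.

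**Model.** For participant i, Y_i = X_i β + e_i with Var(e_i) = Σ (3×3, REML). The model-based variance is C = (Σ_i X_i′ Σ̂⁻¹ X_i)⁻¹. Kenward-Roger replaces C by a larger matrix that allows for estimating Σ. For a single contrast its degrees of freedom equal Satterthwaite's, and only the SE differs.

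**Reference distributions.** The SAP names none, so two t references are shown: n−1 = 29, and within-participant 90 − 30 − 2 − 2 = 56 = 2n−4.

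**Reproducing the nominal 5%.** At n = 240 (2,000 null trials) every t-based and Kenward-Roger test gave 4.8–5.2%. The code therefore returns the planned level when the sample is large.

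**Null simulation of 75/2.5 vs placebo, 30 complete participants, correlation 0.6, 8,000 trials**

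| Covariance | SE ratio (model/true) | t(29) | t(56) | Satterthwaite | Kenward-Roger |
|---|---|---|---|---|---|
| By visit | 0.883 | 7.9% | 8.5% | 8.4% | 5.6% |
| By treatment | 0.986 | 5.4% | 6.0% | 5.4% | 5.4% |
| Random intercept | 0.986 | 4.9% | 5.2% | 5.2% | 5.2% |

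Over correlations 0.5, 0.6 and 0.8, visit indexing gave 7.1–7.9% with t(29), 7.6–8.5% with t(56), 7.6–8.4% with Satterthwaite and 5.0–5.6% with Kenward-Roger, with the SE 10–12% low. With t references, and including designs with fewer participants or with dropouts, treatment indexing gave 4.7–6.1% and the random intercept 4.2–5.5%.

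**Replication.** A separately coded run (20,000 trials per setting; correlation 0.2, 0.5 and 0.8, plus variances rising by visit) gave, for visit indexing with 30 complete, 7.2–7.7% with t(29), 7.8–8.2% with t(56), 7.8–8.2% with Satterthwaite and 5.2–5.5% with Kenward-Roger. A smaller run (4,000 trials, correlation 0.5, Monte Carlo SE about 0.4 points) gave 8.3% and 8.7% for the two t references. The result depends little on the correlation.

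**Hand check.** With an SE ratio of 0.89, the effective critical value is 2.045 × 0.89 = 1.820 for t(29) and 2.003 × 0.89 = 1.783 for t(56). The two-sided tail beyond 1.820 is 6.9% (normal) to 7.9% (t(29)). Beyond 1.783 it is 7.5% (normal) to 8.0% (t(56)). The short SE accounts for essentially all of the excess.

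**Partial dropout.** The mITT set keeps anyone who took a dose and "have at least 1 measurement on the primary endpoint", so partial data stay in. Since 6/30 is exactly 20%, five is the largest number within the plan's assumption. Visit indexing with five partial dropouts gave 8.1% (t(n−1)) and 8.6% (t(2n−4)). Six gave 7.9–8.4% and 8.7–8.9%, with the SE 12–13% low.

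**Cholesky fallback.** It describes the same unstructured matrix, so it does not cure the uncorrected SE. Under visit indexing, the Kenward-Roger adjustment in that parametrization raised the SE by 7–8% instead of 10–12%. The error was 5.9% with 30 complete and 6.4–6.5% with five or six dropouts, against 5.3–5.6% under the plain form.

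**The case against.** The strongest reply is that the inflation needs two things the SAP never states: residual indexing by visit, and an uncorrected SE. The phrase about nesting within treatment sequence identifies the participant, not the matrix index. SAP 6.1 equates visit with period for the fixed effect, not for the covariance. A programmer could index by treatment or choose Kenward-Roger without departing from the text. This stands. A reader might infer that the primary test is known to run at 7–8.5%; the documents do not support that. They support only that the error rate is not fixed by the plan.

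A reader might also quote figures of 8–10%, which arise when 24 complete participants are simulated. Those discard partial data that the mITT set retains, so they describe no planned analysis and are not relied on here.

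It can further be said that the correlations and normality are assumed. That is true, but the error barely moves over correlations from 0.2 to 0.8. The dropout, unequal-variance, interval-width and power figures have had less replication than the complete-data error rates and should carry less weight.

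**Conclusion.** The point holds as an under-specification with a measurable consequence. On the most natural reading, visit indexing with an uncorrected model-based SE, the primary test exceeds its stated two-sided 0.05 by about 2 to 3.5 percentage points with 30 complete participants, and the 95% intervals are too narrow. On the other two readings there is no material problem. The size rests on normal errors, equal variances across nights in the main runs, and the assumed correlations.

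It should be fixed, because the choice would otherwise be made in programming, possibly with results in view. Confidence is medium, since the code that will be run is not specified. Two weaker repairs may look sufficient and are not: Satterthwaite degrees of freedom leave the short SE untouched, and Kenward-Roger with visit indexing comes near 5% without quite reaching it.

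**What to change.** Before unblinding, amend SAP 4.7 for all Gaussian models:

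- State that the unstructured matrix is a residual (R-side) matrix within participant, indexed by treatment.
- Specify `DDFM=KENWARDROGER`, so that the SE is adjusted as well as the degrees of freedom. Simulated error is then about 5% (4.7–5.4% in the equal-variance runs).
- If visit indexing is kept, Kenward-Roger is essential and leaves about 5–6%. It is the weaker choice if variances differ by treatment: with assumed SDs of 0.7, 0.85 and 1.0 for 75/2.5, 37.5/2.5 and placebo, the error was 5.8–6.7% by visit and 4.6–4.9% by treatment.
- If a fit falls back to the Cholesky parametrization, keep the same index and the Kenward-Roger adjustment, and note that under visit indexing the correction may be slightly less complete.

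A participant random intercept with Kenward-Roger could be added as a sensitivity analysis.

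The cost is one or two sentences and one SAS option. Relative to uncorrected intervals, widths grow by under about 2% with the treatment index, or about 8–10% with the visit index. In one power run (correlation 0.6, 30 complete, effect 0.466 SD), where the random intercept with Kenward-Roger had 80% power, treatment indexing with Kenward-Roger had 78% and visit indexing 76%.
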